Adenomyosis is a benign but progressing medical condition characterized by the growth of endometrial cells within the uterine wall and is prevalent in 20-35% of women in the general population¹. The endometrial cells misplaced in the uterine wall are completely functional and will bleed during every menstrual cycle^{2]} thus causing pelvic pain and discomfort. Hormonal factors, parity, age, and uterine abrasion are thought to influence the development of adenomyosis. Patients with adenomyosis are most often between the ages of 35 and 50^{3]} and commonly report dysmenorrhea, menorrhagia, dyspareunia, chronic pelvic pain and infertility.

Adenomyosis can be focal or diffuse and is often associated with other uterine conditions such as fibroids, endometriosis, and/or endometrial polyps. Focal adenomyomas may be mistaken for a uterine fibroid during imaging. Upon imaging or surgical removal, the uterus generally appears larger than normal, particularly when the disease is diffuse where it is described as “bulky” or “heavy”.^[4]

The junctional zone, also called the “inner myometrium” is thought to play a role in the development and diagnosis of adenomyosis. Thickening, enlargement, invasion, or disruption of this junctional zone are “markers” for adenomyosis during magnetic resonance imaging (MRI) or transvaginal ultrasound (TVUS). In addition to this thickening, findings such as anterior/posterior wall asymmetry, echogenic linear striations, or myometrial cysts may be present.^{[4][5][6]} Doppler ultrasound can also be used to look for circumferential blood vessels that are characteristic of fibroids vs adenomyomas that have vessels found within the lesion.^{[7][8]} A definitive diagnosis for adenomyosis is obtained through the examination of uterine tissue following a uterine biopsy or hysterectomy. Under the microscope, the pathologist looks for clusters of endometrial tissue within the myometrium and if the depth of invasion is between 2.5 and 8mm, adenomyosis is confirmed.^[4]

The definitive treatment for adenomyosis is hysterectomy though patients may respond to the administration of non-steroidal anti-inflammatory drugs for pain relief. Reproductive hormones and hormone modulators such as the Mirena IUD ^[9] may help to reduce menstrual pain and bleeding. Other hormonal treatments that have been used with some

level of pain relief and disease regression are oral contraceptives, progestins, and GnRH agonists.

The surgical options for treatment are generally classified as uterine-sparing or non-uterine sparing. The non-uterine-sparing approach is hysterectomy and, as stated above, is the only definitive treatment for adenomyosis. Uterine-sparing procedures such as uterine artery embolization (UAE) have been used to provide some improvement in menstrual bleeding and pain. However, 26% of women undergoing UAE later require a hysterectomy. [4] Other uterine-sparing surgical options include myometrial or adenoma resection, myometrial electrocoagulation, endometrial ablation, myometrial reduction, or magnetic-resonance focused ultrasound. [4]

One proposed method of focal ablation for the treatment of adenomyomas has been used successfully in the treatment of uterine fibroids, providing long term relief of fibroid-related symptoms: laparoscopic radiofrequency ablation, or LAP-RFA. [10][11] In the process of enrolling subjects in an FDA-regulated trial, investigators often encountered women who presented with adenomyomas or diffuse adenomyosis and who, based on exclusion criteria, were not eligible to be treated in the trial. [Personal communication] Several surgeons proposed LAP-RFA as a viable method of treating focal adenomyosis/adenomyomas. The objective of this study is to observe the effects of RFA on adenomyosis through the pathological analysis of the treated tissue that has been removed during a planned hysterectomy.

Experimental Procedures

At the time of the subject's trans-abdominal or laparoscopic hysterectomy, the ProVu System will be used to apply RF treatment to one or two adenomas, focal areas of adenomyosis, or diffuse adenomyosis. Women who require a hysterectomy do not normally undergo this procedure.

Endpoints

The endpoint of this study is the pathological analysis of the treated tissue after application of RF treatment.

Sample Size

Up to twenty (20) subjects will be expected to complete this study. We expect that enrollment of up to 40 subjects may be necessary due to the requirement for a baseline MRI to verify, locate and "map" the adenomyosis/adenomyomas.

Number of Sites

One site will participate. Site will be required to receive study approval from the Institutional Review Board (IRB) prior to study inception. Study enrollment will not begin until IRB approval is obtained.

Design

This is an open-label, prospective, non-randomized, non-controlled study designed to obtain pathology results from the treatment of adenomyomas and/or adenomyosis using a system designed for the ablation soft tissue including symptomatic fibroids.

A. *Screening*

The standard pre-screening for hysterectomy eligibility is expected to be completed before patients are referred to the investigator. Upon referral and following consent, the investigator will review the subject's files and images to determine if the initial inclusion/exclusion criteria have been met.

B. *Blinding*

Blinding will not be appropriate for this study. The subjects and investigators will be informed regarding the use of the system.

C. *Randomization*

Subjects will not be randomized.

D. *Baseline measurements*

After the initial screening of the patient's records including imaging results, both a pre-operative endometrial biopsy (standard of care) and Magnetic Resonance Imaging (MRI) will be performed (if not previously performed within 12 months) to verify enrollment criteria and locate/measure the adenomyosis/adenomyomas.

E. *Exposure assignments*

The length of time that the subject will be exposed to the ProVu System is as follows:

| Period of exposure to the device | Number of subjects exposed |
|----------------------------------|----------------------------|
| < 30 minutes | ≤ 20 |

F. *Follow-up*

Subjects will be followed for safety postoperatively for 6 +/- 2 weeks. The subject's participation in this study ends at the conclusion of the postoperative visit.

Subjects

A. *Selection Criteria*

The criteria listed below shall be used to determine if a participant is eligible for entry into the study.

Inclusion Criteria: Women who are/have

- planning to undergo an abdominal, laparoscopic, or robotic-assisted hysterectomy due to benign conditions,
- uterus \leq 16 weeks gestational size if undergoing a laparoscopic or robotic procedure (no size limit for patients planning to undergo a transabdominal hysterectomy),
- at least one area of focal or diffuse adenomyosis or adenomyomas that is/are contralateral to any fibroids as determined by MRI,
- able to provide informed consent,
- suitable candidates for surgery (have passed a standard pre-operative health assessment),
- English speaking.

Exclusion Criteria: Women who:

- require emergent hysterectomy or vaginal hysterectomy,
- have a uterus $>$ 16 weeks gestational size if undergoing a laparoscopic or robotic procedure (no size limit for patients planning to undergo a transabdominal hysterectomy)
- have fibroids in the proximity of the target adenomyosis (same side, similar location),
- are not appropriate surgical candidates as determined during pre-operative health assessment,
- are unable or unwilling to undergo a hysterectomy,
- are pregnant or lactating,
- are under the age of 18 years,
- have active pelvic inflammatory disease,
- have a history of gynecologic malignancy within the past 3 years,
- are unable to give informed consent, or
- have an implantable uterine or fallopian tube device for contraception
- are not English speaking.

If the subject has been found to have one or more exclusion criteria even after enrollment, the subject will be withdrawn from the study prior to the RF ablation procedure.

B. Identification

The investigator shall assign an identification code to each subject; all data forms and images shall identify the subject by this identification code only.

C. Informed Consent

If a subject meets the inclusion/exclusion criteria, the investigator will explain the conditions of the study. The informed consent documents shall be approved by the IRB prior to use. Informed consent shall be obtained under the conditions as follows:

1. The Principal Investigator or a member of the clinical staff to whom the Principal Investigator may have delegated this responsibility, will

provide the subject with a thorough explanation of the study design, its procedures, expected benefits and potential risks, and all pertinent aspects relative to protection of subjects' safety, wellbeing and confidentiality. During this process, the subject will be allowed to ask all the questions she may have and will receive answers to such questions to her satisfaction. The consenting process will be documented in the subject's study file with a physician's note.

2. the subject shall have sufficient opportunity to consider participation in the study,
3. informed consent shall be obtained without coercion or undue influence,
4. informed consent shall be written in English,
5. a subject will not be led to believe that she is waiving her rights as a subject.

D. Enrollment Timeline

Enrollment occurs when the subject successfully completes the pre-operative health assessment procedures, has met all inclusion/exclusion criteria, and has signed the informed consent document. Study participation ends when the subject has completed her hysterectomy and postoperative period (6 +/- 2 weeks) *or* if the subject withdraws or has been withdrawn from the study prior to her hysterectomy.

E. Treatment

1. All subjects will be under general anesthesia per institutional guidelines.
2. Standard sterile preparation and operative technique will be used.
3. Intraoperative ultrasound will be used to locate target areas of adenomyosis prior to treatment, measure the volume of tissue to be treated, and to guide the placement of the treatment probe.
4. The ProVu treatment probe will be energized and RF energy delivered in a pre-programmed, controlled method based on the predetermined size of the affected tissue.
5. Information on all treated tissue regarding location, morphology, size, deployment, generator mode, treatment temperature, and treatment time will be documented.
6. The treatment probe will be removed and the site assessed for hemostasis.
7. All hysterectomies will be performed according to standard surgical practice.
8. All tissue will be excised with minimal disruption at the time of surgery and will be sent to the hospital pathologist or a core laboratory for assessment.
9. All subjects will exit the study at the time of the postoperative follow up.
10. All other medical care shall be in accordance with accepted medical practice.

F. Subject Compliance

All subjects entering the study are expected to have agreed to a hysterectomy due to pre-existing conditions and to have passed a standard pre-operative health assessment.

G. Subject Discontinuation or Withdrawal

The investigator may withdraw the subject at any time if it is in the subject's best interest. Subjects may voluntarily withdraw from the study at any time without reason. The investigator shall complete a study exit case report form.

H. Compensation and Costs for Study Participation

Subjects will be offered compensation of \$300 for their participation in the study. Subjects will not be required to pay for any of the study procedures or materials during the course of this study. The study grant will not cover non-medical costs or complications that are a result of the standard surgical procedure.

I. Contact for Scheduling

Phone contact for appointment reminders and/or mailed pre-operative instructions prior to surgery dates will be the primary methods of contact.

J. Visit Schedule

The initial screening will be conducted using patient records, prior imaging results, and visit notes. Once subjects have consented to be in the study, they will have an MRI from which the diagnosis of focal or diffuse adenomyosis/adenomyoma is confirmed and lesions are measured. All MRIs will be read by one central radiologist. An endometrial biopsy is standard of care and may have been performed prior to enrollment. (Refer to Table I.)

TABLE I: VISIT SCHEDULE:

| | Screening/Enrollment Visit | Surgery Day | Follow Up 6 +/- 2 weeks Post Op |
|---|----------------------------|-------------|---------------------------------|
| Pre-op Health Assessment Based on Medical Records, Review of Prior Imaging Results (TVUS and/or MRI) | X | | |
| Informed Consent | X | | |
| Magnetic Resonance Imaging (to verify and measure diffuse or focal adenomyosis/adenomyomas), if not performed within the last 12 months | X | | |
| Endometrial Biopsy (standard of care) within 12 months | X | | |
| Pregnancy Test (standard of care) within 24 hours | X | x | |
| Device Use at Surgery | | x | |
| Adverse Event Form | | x | x |
| Study Exit | | | x |

Study Device and Procedure

The ProVu™ System (Hologic, Inc., Boston, MA) is designed and cleared by the FDA as a treatment method for soft tissue, including the treatment of symptomatic uterine fibroids. After locating the general region of the target tissue, a laparoscopic ultrasound transducer is placed on the serosal surface of the uterus to identify the size, location, and number of focal adenomyosis (or adenomyomas). Under ultrasound guidance, the treatment probe (handpiece) is inserted through the serosal surface and into the target tissue. The electrode array containing multiple thermocouples is then deployed according to the size of the target tissue and the position is verified using the ultrasound transducer. Once correctly placed, the surgeon initiates ablation by pressing the foot pedal. Continuous temperature feedback is displayed on the generator screen. For safety purposes, dispersive pads are placed on the patient's thighs to disperse electrical current. If the target tissue is irregular or large, the needle array is retracted and the probe repositioned within the same area under ultrasound

guidance. The ablation is repeated until the area of interest is ablated. Overlapping ablations may be required. At the conclusion of the final ablation, the surgeon retracts the array withdraws the probe through the serosal surface of the uterus while coagulating the track to avoid bleeding. Once hemostasis is confirmed and all target tissue has been treated, the surgeon proceeds with the planned hysterectomy and the tissue is examined by a pathologist to assess the ablation zones within the adenomyoma or focal adenomyosis.

Device Training

All investigators will have completed training on the ProVu system prior to enrollment in this study.

Risk Assessment

A. *Standard surgical risks*

Participation in the study does not eliminate the standard risks of hysterectomy. These include, (but are not limited to), nausea, vomiting, pain, bleeding, infection, poor healing, hernia formation, temporary change in bowel or bladder function, formation of adhesions, air in tissue or abdominal cavity, bleeding at incision sites(s) or abdominal wall, vasovagal reactions, heart attack, fever, infection, and inflammation in the abdomen. Unexpected reactions can occur from any drug or anesthetic that is administered. Unintended injury may occur to other pelvic or abdominal structures such as fallopian tubes, ovaries, uterus, bladder, ureter, bowel, or large blood vessels. Such injury may require immediate surgery or may require surgery at a later time. Dangerous blood clots may form in the legs or lungs. Participation in this study is not expected to alter the likelihood of occurrence or severity of any of these standard surgical risks.

B. *Device risk*

A significant-risk (SR) device study is defined by the United States Food and Drug Administration (<https://www.fda.gov/media/75459/download>) as one that:

- Is intended as an implant and presents a potential for serious risk to the health, safety, or welfare of a subject;
- Is purported or represented to be for use supporting or sustaining human life and presents a potential for serious risk to the health, safety, or welfare of a subject;
- Is for a use of substantial importance in diagnosing, curing, mitigating, or treating disease, or otherwise preventing impairment of human health and presents a potential for serious risk to the health, safety, or welfare of a subject;
- or otherwise presents a potential for serious risk to the health, safety, or welfare of a subject.

A Non-Significant Risk (NSR) device study is one that does not meet the definition for an SR device study. This study poses no significant risks to subjects due to the planned hysterectomy. Risks associated with the device include minimal bleeding

that is no greater than that experienced during pelvic surgery. Bleeding can be easily identified and corrected during the hysterectomy. If bleeding is encountered, it will be managed and the hysterectomy would proceed as planned. The risk of infection from this device or procedure is not expected to be any greater than the risk of infection following a hysterectomy.

Risks associated with the use of radiofrequency ablation in this study are minimal due to the laparoscopic or direct visualization technique utilized in this study. In addition, ultrasound is used to locate and observe regions within the uterus that are not easily visualized directly. The dispersive electrodes on the ProVu System are designed to monitor temperature at three locations of dispersive pad and therefore risks of skin burns are minimized.

C. *Physical risks and discomforts.*

The subjects will undergo normal medical care in every respect except that additional pre-operative screening (MRI) will be provided and the ProVu System will be used immediately prior to the scheduled hysterectomy. The use of the ProVu System will add approximately 30 minutes of anesthesia time. The additional anesthesia time is not considered significant. This study is considered to be non-significant risk (NSR) because the hysterectomy has been planned and only 30 minutes of additional anesthesia time is required to complete the ablation procedures.

D. *Other risks-confidentiality*

Every effort will be made to maintain subject confidentiality. Subjects will be identified primarily by their case report form (CRF) code in the records and databases kept by the company. All the CRFs in which study data are maintained will be coded to disguise any of the subjects' personal information that is unrelated to the study. We cannot guarantee complete confidentiality as subject data may need to be made available to treating medical personnel, Hologic, Inc. or other authorized outside agencies such as the United States Food and Drug Administration (FDA).

E. *Treatment and compensation for injury.*

If the subject is injured as a result of participating in the study, the subject will be treated appropriately until the resolution or stabilization of the injury. The investigator will immediately notify the manufacturer of the occurrence. If it is determined that the ProVu System is responsible for the subject's physical injury, the manufacturer may cover the cost of treatment for the injury. The manufacturer will not cover non-medical costs or indemnification other than may be required by law. Refer to the ProVu System "Instructions for Use" for all warnings and precautions.

Benefits

This is a feasibility protocol for research into the effects of radiofrequency ablation on adenomyosis in women who are already planning to have a hysterectomy. Therefore, there is no expected direct benefit to the subjects enrolled in this study. Other women may benefit from the use of the ProVu System in the treatment of adenomyosis in the future. Society will benefit if it is established that this System design is appropriate for use in a larger population.

Study Adverse Events

A. Definitions

An *adverse event* is any undesirable medical occurrence or untoward deviation in health away from baseline. An *unanticipated* adverse event is one that is not identified in nature, severity, or frequency in the current instructions for use and informed consent. A *device related* adverse event or adverse effect is one that is either definitely, probably, or possibly a result of device use. A *Serious Adverse Event* is any AE that is fatal, immediately life-threatening (i.e., presents an immediate risk of death at the time of the AE, not an AE that hypothetically might have caused death if it were more severe), requires or prolongs in-patient hospitalization, causes permanent or significant disability, requires medical or surgical intervention to prevent permanent sequelae, or any of the outcomes listed above.

B. Investigator Records

The investigator shall categorize adverse events according to the following scale:

- ☐ 1. Definitely device related
- ☐ 2. Probably device related
- ☐ 3. Possibly device related
- ☐ 4. Probably not device related
- ☐ 5. Definitely not device related

C. Investigator Reports

The investigator shall report all adverse events that are unanticipated and are device related to the manufacturer by telephone immediately upon becoming aware of them. A follow-up written report shall be emailed to the manufacturer within 24 hours and shall include the following information:

- i. Nature of adverse effect
- ii. Statement as to why it is considered unanticipated
- iii. Statement as to the degree to which it is considered device related, and why
- iv. Results of any diagnostic tests that were performed
- v. Description of any treatment implemented

- vi. Statement of subject's current clinical status
- vii. Investigator's signature and date

The investigator shall supply a copy of the report for adverse events that are serious or unanticipated and device related to the reviewing IRB.

The investigator shall continue to clinically monitor the adverse effect, with laboratory tests if appropriate, until it is resolved, stabilized or returns to baseline.

Confidentiality

Research records are marked by subject number and initials. Subject research files, including signed consent forms, will be kept in locked cabinets at the study site. All information provided to the Investigator by the manufacturer, or its designates, including non-clinical data, protocols, CRFs, and verbal and written information, will be kept strictly confidential and confined to the research staff involved in conducting the study. It is recognized that this information may be related in confidence to the IRB. Subjects' records will be made available to regulatory authorities as required.

Documentation

Accurate, complete and timely documentation is essential to the successful conduct of this study.

A. Investigator Responsibility

The investigator is responsible for maintaining the following documentation as updated and complete as possible at all times:

1. Informed consents.
2. Case report forms.
3. Adverse effect reports to the manufacturer.
4. Adverse effect reports to IRB.
5. Photographs, videos, images, if any.
6. Material control logs.
7. Screening logs.
8. IRB approval for protocol.
9. IRB approval for informed consent.
10. Final report to the IRB and manufacturer, in addition to any other reporting requirement that may be requested.
11. Records of deviations, violations and amendments.
12. Protocol (including all revisions).
13. Regulatory Binder.
14. Agreement Letter and Study Site Contract.
15. All correspondence relating to study.

Quality Assurance:

A. *Data Quality Assurance*

Steps to be taken to assure the accuracy and reliability of data include review of protocol procedures with the investigator and associated personnel prior to the study. Case report forms will be reviewed for accuracy and completeness as compared with the source documents.

B. *Monitoring*

Monitoring will be performed according to Good Clinical Practices (GCP) guidelines established by the United States Food and Drug Administration (FDA). A Contract Research Organization (CRO) may be used to monitor the study. Monitoring will be scheduled in accordance with recruitment/enrollment rates and site performance requirements.

C. *Data Management*

After monitoring of the data is complete, data will be entered into the database by a third-party data manager.

Data Analysis

Data analysis will consist of the evaluation of the ProVu System performance relative to the proposed use, prescribed treatment, pathology results and adverse device effects. Descriptive statistics (including those derived from pathology results, see Appendices A-C) will be provided as dictated per protocol. A full statistical analysis will not be appropriate considering the size and intent of this study.

Personnel Responsibilities

The investigator will assign a study coordinator to assist during the conduct of this study. There are no other required site personnel.

Return of Unused Inventory

All unused System handpieces shall be returned to the manufacturer. Used electrodes will be disposed of according to hospital standards for biohazard materials. Any generators, cables, and other non-disposable parts that are donated for use during this study will be returned to the manufacturer at the conclusion of the study.

References

1. <https://en.wikipedia.org/wiki/Adenomyosis>
2. Gunther R, Walker C (2020). "Adenomyosis" StatPearls [Internet]. Treasure Island (FL): StatPearls Publishing; 2020 Jun 24. PMID 30969690.

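### Early end of participation is tied to the hysterectomy although device exposure starts before it, so an exposed woman who is withdrawn can lose the scheduled 6 +/- 2 week safety observation

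*Protocol*

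**What the plan says.** Subjects, D. Enrollment Timeline gives two ways for participation to end. One is completion of the hysterectomy and the postoperative period. The other is early: "if the subject withdraws or has been withdrawn from the study prior to her hysterectomy".

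Elsewhere the Protocol describes follow-up and exit without that exception. Design, F. Follow-up states: "Subjects will be followed for safety postoperatively for 6 +/- 2 weeks". Subjects, E. Treatment, item 9 states: "All subjects will exit the study at the time of the postoperative follow up". Table I puts the Adverse Event Form on the surgery day and at the follow-up visit, and puts Study Exit at the follow-up visit only.

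On the order of events, Risk Assessment, C. Physical risks and discomforts says that "the ProVu System will be used immediately prior to the scheduled hysterectomy". Study Device and Procedure describes the same sequence: "Once hemostasis is confirmed and all target tissue has been treated, the surgeon proceeds with the planned hysterectomy".

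On withdrawal, Subjects, G. Subject Discontinuation or Withdrawal says: "The investigator may withdraw the subject at any time if it is in the subject's best interest". It gives subjects the same freedom and asks for an exit form. Subjects, A. Selection Criteria uses a different limit: a subject found after enrollment to meet an exclusion criterion is to be withdrawn before the RF procedure.

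**The concern.** For safety purposes the relevant moment is first exposure to the device. Section D uses a later moment, the hysterectomy, as the limit for early exit. Between the two lies a short interval in which a woman has been exposed but has not yet had the operation that the exit rule refers to.

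That interval bears on the Protocol's own risk argument. Risk Assessment, B. Device risk reasons: "This study poses no significant risks to subjects due to the planned hysterectomy". The argument is weakest for an exposed woman whose hysterectomy does not follow, and she is the one whose scheduled observation section D would end if she were withdrawn. Adverse device effects are a named part of the Data Analysis section and the exposed group is at most 20 women, so each exposed woman is worth keeping under observation.

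**Working it through.** The Protocol states no figure on this point and no arithmetic applies. The check applies the rules to each path a subject can take.

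1. **Withdrawn before RF.** She was never exposed. Section D ends her participation, and no safety observation of the device is lost.
2. **RF, then hysterectomy, no withdrawal.** Section D, Follow-up and item 9 agree: she is followed for 6 +/- 2 weeks (weeks 4 to 8) and exits at that visit.
3. **RF started, hysterectomy abandoned or deferred, not withdrawn.** The early-exit limb of section D is not triggered. Follow-up, item 9 and Table I still apply.
4. **RF started, hysterectomy abandoned or deferred, then withdrawn.** Section D ends her participation, because she has been withdrawn before her hysterectomy. Follow-up and item 9 say she is followed and exits at the postoperative visit. These statements cannot all hold.
5. **RF and hysterectomy done, then withdrawn before the visit.** Section G permits this. Section D does not list it, item 9 does not recognise it, and nothing says whether adverse events are still collected.

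Path 4 carries the contradiction. It can be reached in only a few ways:

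- A late-found exclusion criterion does not lead there, because that withdrawal must come before RF.
- The woman cannot withdraw herself between RF and an immediately following hysterectomy: "All subjects will be under general anesthesia per institutional guidelines".
- The investigator can withdraw her, since section G permits this at any time.
- If the hysterectomy is deferred, she wakes and may withdraw under section G, still before her hysterectomy.

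What remains for her on path 4:

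- Risk Assessment, E requires an injury from participation to be treated until it resolves or stabilizes.
- Study Adverse Events, C. Investigator Reports requires continued clinical monitoring of an adverse effect to resolution, stabilization or baseline.
- Both presuppose a known event. What is lost is the scheduled contact and the follow-up Adverse Event Form, which would pick up a new or later-detected event.

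**The case against.** The strongest reply is that the situation is remote and the wording open to a milder reading. Experimental Procedures places device use at the time of the hysterectomy. On that wording the RF step belongs to the hysterectomy session, and withdrawal before hysterectomy simply means before surgery. RF adds only about 30 minutes to a single anesthetic. An abandoned hysterectomy does not itself end participation, and nothing obliges the investigator to withdraw the woman. All of this stands, and it makes the event uncommon. It does not settle the text, because Risk Assessment, C puts the device before the hysterectomy and Selection Criteria treats RF as a limit of its own.

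Three stronger readings are tempting, and the Protocol does not support them:

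- **A reader might infer that she would have no safety follow-up at all.** Known injuries and adverse effects are still followed, so only the scheduled search for further events is lost.
- **A reader might infer that the exit rule costs the study her endpoint.** The endpoint is pathology of the treated tissue. Without an excised uterus there is none, whatever the participation rule says.
- **A reader might infer that she drops out of the denominator and that safety results are therefore biased in the device's favour.** No section excludes withdrawn subjects from the description. Analysis sets are commonly left to a statistical analysis plan, which was not available for this review. Any before-and-after event rate would rest on assumptions about both the event and the denominator.

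**Conclusion.** The point holds as a misplaced cut-off that contradicts other stated rules. Read literally, section D lets a woman in whom RF was started, and who is withdrawn before a hysterectomy that was abandoned or deferred, leave before the 6 +/- 2 week safety observation that Follow-up and item 9 set for subjects generally.

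The consequence is limited to new or later-detected adverse events in such a woman. The conclusion rests on the literal reading of section D and on an actual withdrawal taking place. The Protocol gives no probability for the sequence, so no effect on the safety results can be calculated. At full enrollment one woman is 1/20 = 5% of those exposed. That is the weight of a single subject, not an estimate of the loss. The amendment is worth making because it is cheap and protects detection of harm in exposed women, not because a material distortion has been shown.

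**What to change.** Reconcile Design, F; Subjects, A (the withdrawal sentence); and Subjects, D, E item 9 and G, so that:

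- early end of participation applies only to subjects withdrawn before RF energy is first delivered;
- for every subject in whom RF has started, and with her agreement, adverse events are collected to the Protocol's existing 6 +/- 2 week point, from records or by telephone if she does not attend, whether or not the hysterectomy took place and whether or not she is withdrawn;
- all RF-started subjects are counted in the description of adverse device effects.

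This concerns data collection only and leaves clinical management as it is. A full Appendix A work-up should not be required after a deferred hysterectomy. The Pathology section needs the uterus received, and the viability stain (TTC) assessed, within four hours of treatment, and it treats the histology as a same-day specimen.

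The cost is a few sentences of amendment, matching consent text, an occasional extra call or record check, and possibly a less favourable safety table.
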